7.1.1. Analysis Timings

Analyses (immunogenicity or safety) may be performed at any time (eg, safety data through approximately 1 week after vaccination) for participants 18 through 64 years of age.

Complete safety and immunogenicity analyses will be performed at the end of this substudy.

7.2. Interim Analyses and Summaries

No formal interim analysis will be conducted for this study.

9. APPENDICES

Appendix 1. List of Abbreviations

Abbreviation	Term
AE	adverse event
bIRV	bivalent influenza modRNA vaccine
BLQ	below the limit of quantitation
BNT162b2	Pfizer-BioNTech COVID-19 vaccine
CI	confidence interval
COVID-19	coronavirus disease 2019
CRF	case report form
ECG	electrocardiogram
e-diary	electronic diary
GMFR	geometric mean fold rise
GMR	geometric mean ratio
GMT	geometric mean titer
HAI	hemagglutination inhibition assay
ICD	informed consent document
IPM	investigational product manual
IRC	internal review committee
IRT	interactive response technology
IRV	influenza modRNA vaccine
IV	intravenous
LLOQ	lower limit of quantitation
LOD	limit of detection
LS	least square
MCAR	missing completely at random
MedDRA	Medical Dictionary for Regulatory Activities
mITT	modified intent-to-treat
modRNA	nucleoside-modified messenger ribonucleic acid
N/A	not applicable
Omi	Omicron
PT	preferred term
qIRV	quadrivalent influenza modRNA vaccine
QIV	quadrivalent influenza vaccine
RCDC	reverse cumulative distribution curve
SAE	serious adverse event
SAP	statistical analysis plan
SARS-CoV-2	severe acute respiratory syndrome coronavirus 2
SOC	system organ class
tIRV	trivalent influenza modRNA vaccine
VOC	variant of concern
WHO	World Health Organization

Appendix 2. Reactogenicity Data Consolidation

For reactogenicity collected in the e-diary, redness and swelling will be measured and recorded in measuring device (caliper) units, and then categorized during analysis as mild, moderate, or severe based on the grading scale in Table 3. Measuring device units can be converted to centimeters according to the following scale: 1 measuring device unit = 0.5 cm. Pain at the injection site will be assessed by the participant as mild, moderate, or severe according to the grading scale in Table 3. The systemic events of fatigue (tiredness), headache, muscle pain, vomiting, diarrhea, chills, and joint pain will be assessed by participants as mild, moderate, or severe according to the grading scale in Table 4. Grade 4 reactions and events, which can only be classified by an investigator or medically qualified person, will be collected as AEs on the CRF. For reactogenicity collected in the AE CRF, the grading scales will be based on the AE intensity scale in Table 5. If a local reaction or systemic event is captured in more than 1 data source, eg, the e-diary, unplanned assessments, and/or AE CRF, the highest grade will be used in the safety summary analysis.

Table 3. Local Reaction Grading Scale

	Mild (Grade 1)	Moderate (Grade 2)	Severe (Grade 3)	Potentially Life-Threatening (Grade 4)
Pain at the injection site	Does not interfere with activity	Interferes with activity	Prevents daily activity	Emergency room visit or hospitalization for severe pain
Redness	>2.0 cm to 5.0 cm (5 to 10 measuring device units)	>5.0 cm to 10.0 cm (11 to 20 measuring device units)	>10 cm (≥21 measuring device units)	Necrosis or exfoliative dermatitis
Swelling	>2.0 cm to 5.0 cm (5 to 10 measuring device units)	>5.0 cm to 10.0 cm (11 to 20 measuring device units)	>10 cm (≥21 measuring device units)	Necrosis

Table 4. Systemic Event Grading Scale

	Mild (Grade 1)	Moderate (Grade 2)	Severe (Grade 3)	Potentially Life- Threatening (Grade 4)
Vomiting	1-2 times in 24 hours	>2 times in 24 hours	Requires IV hydration	Emergency room visit or hospitalization for hypotensive shock
Diarrhea	2 to 3 loose stools in 24 hours	4 to 5 loose stools in 24 hours	6 or more loose stools in 24 hours	Emergency room visit or hospitalization for severe diarrhea
Headache	Does not interfere with activity	Some interference with activity	Prevents daily routine activity	Emergency room visit or hospitalization for severe headache
Fatigue/tiredness	Does not interfere with activity	Some interference with activity	Prevents daily routine activity	Emergency room visit or hospitalization for severe fatigue

Table 4. Systemic Event Grading Scale

	Mild (Grade 1)	Moderate (Grade 2)	Severe (Grade 3)	Potentially Life- Threatening (Grade 4)
Chills	Does not interfere with activity	Some interference with activity	Prevents daily routine activity	Emergency room visit or hospitalization for severe chills
New or worsened muscle pain	Does not interfere with activity	Some interference with activity	Prevents daily routine activity	Emergency room visit or hospitalization for severe new or worsened muscle pain
New or worsened joint pain	Does not interfere with activity	Some interference with activity	Prevents daily routine activity	Emergency room visit or hospitalization for severe new or worsened joint pain

Table 5. Assessment of AE Intensity Grade

GRADE	If required on the AE page of the CRF, the investigator will use the adjectives MILD,	
	MODERATE, SEVERE,	or LIFE-THREATENING to describe the maximum intensity
	of the AE. For purposes of	of consistency, these intensity grades are defined as follows:
1	MILD	Does not interfere with participant's usual function.
2	MODERATE Interferes to some extent with participant's usual function.	
3	SEVERE	Interferes significantly with participant's usual function.
4	LIFE-THREATENING	Life-threatening consequences; urgent intervention indicated.

Temperatures recorded in degrees Fahrenheit will be programmatically converted to degrees Celsius first for reporting. Fever will be grouped into ranges for the analysis according to Table 6. Maximum temperature range over the period from Day 1 through Day 7 will be mapped into the ranges described in Table 6 for summary of maximum temperature.

Table 6. Scale for Fever

≥38.0-38.4°C (100.4-101.1°F)
>38.4-38.9°C (101.2-102.0°F)
>38.9-40.0°C (102.1-104.0°F)
>40.0°C (>104.0°F)

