8.3.5.2. Local Reactions

Following vaccination (where Day 1 is the day of vaccination), participants will be asked to assess redness, swelling, and pain at the injection site and to record the symptoms in the reactogenicity e-diary daily. In Substudies A and B, local reactions will be assessed at the injection site on the right arm only after vaccinations given at Visits 1 and 201.

If a local reaction persists beyond the end of the reactogenicity e-diary period following vaccination, the participant will be requested to report that information. The investigator will enter this additional information in the CRF.

Participants will be provided with a measuring device. Redness and swelling will be measured and recorded in measuring device units (range: 1 to 21) and then categorized during analysis as absent, mild, moderate, or severe based on the grading scale in Table 4. Measuring device units can be converted to centimeters according to the following formula: 1 measuring device unit = 0.5 cm. Pain at the injection site will be assessed by the participant as absent, mild, moderate, or severe according to the grading scale in Table 4.

If a Grade 3 local reaction is reported in the reactogenicity e-diary, a telephone contact should occur to ascertain further details and determine whether a site visit is clinically indicated. Only an investigator or medically qualified person is able to classify a participant's local reaction as Grade 4. If a participant experiences a confirmed Grade 4 local reaction, the investigator must immediately notify the sponsor.

Table 4.	Local Reaction	Grading Scale
----------	----------------	----------------------

	Mild (Grade 1)	Moderate (Grade 2)	Severe (Grade 3)	Potentially Life-Threatening
Pain at the injection site	Does not interfere with activity	Interferes with activity	Prevents daily activity	(Grade 4) Emergency room visit or hospitalization for severe pain
Redness	>2.0 cm to 5.0 cm (5 to 10 measuring device units)	>5.0 cm to 10.0 cm (11 to 20 measuring device units)	>10 cm (≥21 measuring device units)	Necrosis or exfoliative dermatitis
Swelling	>2.0 cm to 5.0 cm (5 to 10 measuring device units)	>5.0 cm to 10.0 cm (11 to 20 measuring device units)	>10 cm (≥21 measuring device units)	Necrosis

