10.12.6.2.2. Blinding of Site Personnel for Substudy B

Substudy B is single-blind, such that all site personnel, including the investigator, investigator staff, and study staff receiving, storing, dispensing, preparing, and administering the study interventions will be unblinded.

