2.1. Modifications to the Analysis Plan Described in the Protocol

Not applicable.

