3.1.1. Local Reactions and Systemic Events

Local reactions will be assessed at the injection site on the right arm only. Endpoints include both each reaction or event and any reaction or event.

The local reactions, including redness, swelling, and pain at the injection site, and the systemic events, including fever, fatigue (tiredness), headache, muscle pain, vomiting, diarrhea, chills, and joint pain, are reported in the e-diary from Day 1 through Day 7 after vaccination, where Day 1 is the day of vaccination. The e-diary entries from the participant will be the primary data source for these events. However, any related events that are considered local reactions or systemic events starting within 7 days after vaccination, that are recorded in the unplanned CRF or AE CRF, will be consolidated with e-diary data and the data included in the reactogenicity summaries if the participant has any e-diary data recorded.

This section describes derivations with details for the assessment of the reactogenicity data: severity level, duration, and onset day.

Severity and Maximum Severity

The definitions for reactogenicity severity collected from the e-diary and from AEs are described in Appendix 2.

For each local reaction or systemic event after vaccination, the maximum severity will be derived for the collection period (Day 1 through Day 7, where Day 1 is the day of vaccination) as follows:

maximum severity = highest grade (maximum severity) within 7 days after vaccination (Day 1 through Day 7) among severity grades reported for that local reaction or systemic event

Duration (First to Last Day Reported)

The duration (days) of each local reaction or systemic event will be calculated as the number of days from the start of the first reported reaction or event to the resolution of the last reported reaction or event, inclusive. For reactions or events collected in the e-diary, resolution is defined as the last day on which the reaction or event is recorded in the e-diary if the reaction or event lasted 7 days or less, or it is defined as the day on which the reaction or event ended beyond Day 7 (the latter will be collected on the CRF). For reactions and events collected in the AE CRF, the AE end date will be considered the resolution date. For a reaction or event collected in multiple sources, the latest date will be used in calculating the duration. If there is no known resolution/end date, the duration will be reported as unknown or missing.

Onset Day

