5.3. Methods to Manage Missing Data

Standard algorithms on handling missing AE dates will be applied according to Pfizer safety rules. A completely missing start date for an AE is not allowed in data collection. For derived variables based on reactogenicity data, if any day of the 7-day e-diary is available, the "any day (Day 1 through Day 7)" data will be considered nonmissing. It is expected that these reactogenicity events would be queried by the investigator for the missing e-diary days and would be entered in the AE CRF if any reactogenicity was not reported in the e-diary due to missed days. Therefore, the primary analysis will use the reactogenicity recorded in the AE CRF to impute the partially missing e-diary data to estimate the reactogenicity rate during the e-diary collection period. The AE CRF is designed as a log page, which means only events that occurred will be recorded and events that did not occur will not be recorded. Therefore, all remaining missing days are considered as having answered "no." This imputation can reasonably estimate the reactogenicity event rates during the e-diary collection period.

Antibody titers below the LLOQ, denoted as BLQ, or below the LOD will be set to $0.5 \times \text{LLOQ}$ for GMT analysis. No other missing assay data will be imputed in the analyses.

When calculating a fold rise, the assay results will be converted to $0.5 \times LLOQ$ if assay results are < LLOQ, except when the prevaccination assay result is < LLOQ while the postvaccination result is $\ge LLOQ$, in which case the prevaccination value will be set to LLOQ. If both the numerator and denominator are < LLOQ, then both will be converted in the same way.

Values for sera that are insufficient, indeterminate results, or values recorded as "not done" will be set to "missing."

LLOQs for each assay used in this study will be included in serology data transfer once they are available.

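### The Substudy B SAP grades AE-CRF reactogenicity on the general AE intensity scale and keeps the highest grade, so sub-threshold redness, swelling or diarrhea can enter the primary rates and the severity displays mix two scales

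*SAP*

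**What the plan says.** **Diary scale.** Protocol 8.3.5.2 says: "Redness and swelling will be measured and recorded in measuring device units (range: 1 to 21) and then categorized during analysis as absent"; the categories above that go by diameter. Tables 3 and 4 of SAP B Appendix 2 repeat the protocol's scales: diameter for redness and swelling, stool count for diarrhea, episode count or need for IV fluids for vomiting, and effect on activity for pain and the other symptoms. Fever is banded by temperature in Table 6.

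**AE-CRF scale.** Appendix 2 says: "For reactogenicity collected in the AE CRF, the grading scales will be based on the AE intensity scale in Table 5". No item is exempted. Table 5 is purely functional; its severe level reads "Interferes significantly with participant's usual function". Across sources, "the highest grade will be used in the safety summary analysis".

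**When AE-CRF events are used.** SAP B 3.1.1 says that related reactions starting within 7 days and recorded in the AE CRF or the unplanned CRF "will be consolidated with e-diary data and the data included in the reactogenicity summaries if the participant has any e-diary data recorded". SAP B 5.3 is narrower: "the primary analysis will use the reactogenicity recorded in the AE CRF to impute the partially missing e-diary data". Protocol 9.3.1 and 10.12.9.1.1.1 likewise use AE-CRF reactogenicity to fill missing diary entries. SAP B 6.1.1.1 says that missing values are not imputed. SAP B 2.1, on modifications to the protocol's analysis plan, reads "Not applicable".

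**Who grades.** Participants complete the diary and are blinded (Protocol 10.12.6.2.1). Investigators grade AEs (Protocol 10.3.3). Protocol 10.12.6.2.2 says: "Substudy B is single-blind, such that all site personnel, including the investigator", are unblinded.

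**The concern.** Two instruments with different cut-points feed one rate. For items with a measured floor in the diary, an event below that floor becomes present simply because it was recorded on another form. The highest-grade rule then lets a functional AE grade override a diary measurement taken on the same day.

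The AE grade comes from staff who know the allocation, and the diary entry from a participant who does not. If the tendency to write AEs differs between vaccine groups, the comparison of groups absorbs that difference. These are primary safety endpoints, and under Protocol 10.12.4.1 the sponsor's internal review committee uses the 4-week safety data to judge which groups are acceptable for further study.

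Comparability across substudies also suffers. Tables 3 and 4 of the Substudy A SAP explicitly code redness or swelling of 2.0 cm or less as no reaction. The Substudy B SAP has no such presence rule and implies the floor only through the Grade 1 row of its Table 3. The same finding could be absent in Substudy A and present in Substudy B.

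**Working it through.** No figure in the plan is at issue, so the check compares the scales item by item and then sizes one reclassification.

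**1. Scales side by side** (SAP B Appendix 2; 1 measuring device unit = 0.5 cm)

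| Item | Diary: lowest counted level | Diary: severe | What Table 5 can change |
|---|---|---|---|
| Redness, swelling | above 2.0 cm; 5 units × 0.5 = 2.5 cm | above 10 cm; 21 × 0.5 = 10.5 cm | presence and severity |
| Diarrhea | 2 loose stools in a day | 6 or more | presence and severity |
| Vomiting | 1 episode | IV fluids needed | severity only |
| Pain, headache, fatigue, chills, muscle and joint pain | any, without effect on activity | daily activity prevented | severity only |
| Fever | 38.0°C | temperature bands (Table 6) | unresolved only if no temperature is recorded |

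Example: redness of 3 units is 3 × 0.5 = 1.5 cm, below the 5-unit floor, so the diary scale calls it absent. As an AE it is at least Grade 1.

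**2. Where this enters the analysis.** The main result in SAP B 6.1.1.1 is the proportion with each, and any, reaction, not split by grade. Presence gaps (redness, swelling, diarrhea) therefore reach the primary rate. Severity gaps reach the severe-event summaries and the maximum-severity bar charts in 6.1.1.2.

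**3. Direction.** Compared with diary data alone, adding AE-CRF events and keeping the highest grade can only add an event or raise a grade. Compared with applying Tables 3 and 4 to the same event, the direction can reverse:

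- An AE-only redness above 10 cm that leaves function intact is severe by Table 3 and mild by Table 5.
- Appendix 2 sends Grade 4 reactions to the AE CRF and then grades AE-CRF reactions by Table 5. An emergency visit for severe headache is Grade 4 in Table 4 but may be only Grade 3 in Table 5. As written, the Grade 4 columns of Tables 3 and 4 are never applied.

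**4. Size per participant.** The change in a rate is k/n for k reclassified participants; k is not in the documents and is assumed here. Exact Clopper-Pearson 95% intervals, starting from zero events:

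| n | k = 0 | k = 1 | k = 2 |
|---|---|---|---|
| 30 | 0% (0 to 11.6) | 1/30 = 3.3% (0.1 to 17.2) | 2/30 = 6.7% (0.8 to 22.1) |
| 120 | 0% (0 to 3.0) | 1/120 = 0.8% (0.0 to 4.6) | 2/120 = 1.7% (0.2 to 5.9) |

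**The case against.** The other side has a good deal to stand on.

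- Protocol 8.3.5 expects a prompted reaction in the AE CRF only when a diary entry was missed, so overlap with completed diary days should be limited. This stands as an expectation, but SAP B 3.1.1 sets no such limit.
- Table 5 is the scale that the protocol itself prescribes for every AE. That is true, but it does not make its grades interchangeable with the reactogenicity scale.
- SAP B 6.1.1.2 already plans the proportions from diary data alone, so a reader can see how far the rates move. This limits the harm. The analysis is supplementary and is not stated to be by severity.
- The SAP B version history attributes the reactogenicity adjustment to regulatory feedback, and both documents let the SAP modify the protocol. That supports keeping consolidation as the main analysis. The history does not mention the change of scale or the highest-grade rule.
- Unscheduled reaction visits already measure diameters and use the protocol grades (Protocol 10.12.8.9.7), so the problem is confined to the AE CRF.
- The substudy is descriptive, with no hypotheses, and at n = 30 one event is well within the interval width. The stopping rule on repeated Grade 3 events also excludes these reactions wherever they are recorded (Protocol 10.12.8.7).

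Together these points narrow the concern without removing it: a stated rule still gives inconsistent results for the same finding.

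**Conclusion.** The concern holds for presence in redness, swelling and diarrhea. For severity it holds for those items, vomiting and the activity-based symptoms. Consolidating on all days, rather than filling missed entries, goes beyond the protocol and beyond SAP B 5.3, and Section 2.1 does not declare it. The size is 3.3 points per reclassified participant in a group of 30 and 0.8 in a group of 120, with the number of such participants unknown.

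Four stronger readings are tempting and not supported:

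- *Vomiting and fever rates are distorted in the primary analysis.* One vomiting episode is already Grade 1 in the diary, and fever is banded by temperature. The open question for fever is an AE-CRF report without a temperature.
- *Rates and grades always go up.* This is so only against diary-only data; the Grade 4 conflict can lower a grade.
- *Unblinded grading biases the group comparison.* The route exists, but nothing in the documents shows or quantifies differential recording.
- *Consolidation should be demoted to a sensitivity analysis, or unmeasured events taken out of the main rate.* That is a debatable trade-off. The regulatory feedback is not visible, and nothing shows that the AE CRF holds diameters or stool counts.

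**What to change.** Keep the consolidated analysis as the main one and amend SAP B as follows.

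1. On days with a completed diary entry, use the measured diary value for redness, swelling, diarrhea and fever. The exception is a Grade 4 reaction confirmed by the investigator, graded by Tables 3 and 4.
2. Grade AE-CRF events by Tables 3, 4 and 6 wherever a diameter, count or temperature is recorded. Otherwise keep the event in the rate and footnote the number graded by Table 5 only.
3. Produce the planned e-diary-only analysis by maximum severity as well, beside the consolidated display.
4. Reconcile Sections 3.1.1, 5.3 and 6.1.1.1 on which days AE-CRF data are used and whether missing entries are imputed, and declare the departure in Section 2.1.

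The cost is a little more programming and SAP wording. One limit remains: some AE-only events will stay on the Table 5 scale. Groups 1, 3, 4 and 5 were enrolled under a prior protocol version (Protocol 1.2) and may have no measurements to regrade.

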Appendix 3. Dose-Level Combinations for Substudy B

Table 7. Substudy B: qIRV Bivalent BNT162b2 (Original/Omi BA.4/BA.5)
Dose-Level Combination

Dose-Level Combination	qIRV Dose and Strain Combination	Bivalent BNT162b2 (Original*/Omi BA.4/BA.5) Dose ^a	Total modRNA Dose
1ь	CCI ug qIRV containing	CCI μg	CC μg
2 ^d	CCI µg qIRV containing	μg	μg
3 ^b	CCI µg qIRV containing	μg	μg
4 ^b	CCI LIGHT PROPERTY OF THE PROP	μg	μg
5 ^b	CCI ug, qIRV containing	μg	μg

Table 7. Substudy B: qIRV Bivalent BNT162b2 (Original/Omi BA.4/BA.5)

Dose-Level Combination

Dose-Level Combination	qIRV Dose and Strain Combination	Bivalent BNT162b2 (Original*/Omi BA.4/BA.5) Dose ^a	Total modRNA Dose
6 ^b	CCI μg qIRV containing	cc μg	ССІ µg
7 ^b	CCI µg qIRV containing	μg	μg
8 _p	CCI µg qIRV containing	μg	μg

- a. For bivalent BNT162b2 formulations: CC μg total dose includes μg of Omi BA.4/BA.5 and μg of the ancestral SARS-CoV-2 strain; μg total dose includes μg of Omi BA.4/BA.5 and μg of the ancestral SARS-CoV-2 strain.
- b. mIRVs encoding HA for each A and B strain will be CC with to generate qIRV at the dose-level combination shown; the resultant qIRV will then be CC with bivalent BNT162b2 (original/Omi BA.4/BA.5) prior to administration. Please see the IPM for further details.
- c. This A strain will be updated to CCI based on the 2023-2024 northern hemisphere seasonal influenza strain selection.
- d. **CCI** product.

Note: * Original refers to the ancestral strain (Wuhan-Hu-1; USA-WA1/2020), also referred to in the protocol as the reference strain.

Document Approval Record

Document Name:	C5261001 Substudy B Statistical Analysis Plan Clean Copy, V2, 22 Fe b 2024
Document Title:	A PHASE 1/2 MASTER PROTOCOL TO EVALUATE THE SAFETY, TOLERABILITY, AND IMMUNOGENICITY OF COMBINED MODIFIED RNA VACCINE CANDIDATES AGAINST COVID-19 AND INFLUENZA IN HEALTHY INDIVIDUALS – SUBSTUDY B Statistical Analysis Plan (SAP)

Signed By:	Date(GMT)	Signing Capacity
PPD	22-Feb-2024 16:44:47	Final Approval
